### **12.3.6. Open-label Extension Full Analysis Set**

All patients who received at least 1 dose of sparsentan in the open-label extension period will be included in the Open-label Extension Full Analysis Set (OLEFAS). All efficacy and safety analyses during the open-label extension period will be based on the OLEFAS.

### **12.3.7. Sparsentan + SGLT2 Inhibitor Sub-study Analysis Set**

All patients who are randomized in the Sub-study will be included in the Sub-study Analysis Set. All Sub-study efficacy and safety analyses will be based on the Sub-study Analysis Set.

## **12.4. Demographics and Baseline Characteristics**

Demographic data and baseline characteristics for the FAS, PAS, PP Analysis Set, Safety Analysis Set, OLEFAS, and Sub-study Analysis Set will be summarized by treatment group using descriptive statistics.

## **12.5. Patient Accountability and Disposition**

For the double-blind period, patient disposition will be summarized by the numbers and percentages of patients who screened, failed screening, enrolled, were randomized, received randomized treatment, completed randomized treatment, discontinued randomized treatment early (including reasons), completed the study, and discontinued from the study (including reasons). Data will be presented overall and by treatment group.

For the open-label extension period, frequencies and percentages will be displayed for the number of patients who entered the open-label extension period, discontinued open-label treatment, and completed the open-label extension period. Data will be presented overall using the OLEFAS and Sub-study Analysis Set.

The number and percentage of patients in each analysis set will be summarized.

## **12.6. Study Medication Usage and Compliance**

For the double-blind period, compliance rates during the treatment period will be derived using the following formula:

$$100 \times \left( \frac{\text{Total number of capsules dispensed} - \text{Total number of capsules returned}}{\text{Expected number of capsules to be taken based on the patient's titration schedule}} \right)$$

Compliance rates will be summarized for the Safety Analysis Set using summary statistics and numbers and percentages within categories (eg, 0-<20%, 20-<40%, 40-<60%, 60-<80%, 80-<100%, 100-<120%,  $\geq$ 120%) by treatment group and overall.

Duration of treatment in weeks, defined as follows:

$$(\text{date of last dose of study medication} - \text{date of first dose of study medication} + 1)/7$$

will also be summarized by treatment group for the Safety Analysis Set.

For the open-label extension period, compliance will be calculated using an analogous approach as above but using dosage strength instead of number of tablets. Compliance will be summarized overall for the OLEFAS.

The above approaches will be applied to UP/C and eGFR values in the open-label extension period.

## **12.7. Efficacy Analyses**

Efficacy analyses during the double-blind period will be based on the FAS. The primary and key secondary endpoint analyses only will be repeated in the PP Analysis Set as supportive analyses.

As UP/C is a highly right-skewed variable, analyses will be performed on log-transformed data.

The eGFR for each time point (visit) will be determined using the CKD-EPI (Levey 2009) formula for adults based on age, sex, race, and serum creatinine values from the visit. The eGFR will be determined at screening and at assessment time points detailed in the Schedules of Study Events (Section 15.1).

### **12.7.1. Analysis of the Primary Endpoint: Change from Baseline in Proteinuria at Week 36**

After approximately 280 patients have undergone the Week 36 visit, proteinuria (UP/C) data will be analyzed via a mixed-model repeated-measures analysis. Change from baseline during the double-blind period in UP/C on the log scale will be the dependent variable. Log baseline UP/C will be included as a covariate along with fixed effects for randomized treatment, time (ie, nominal visit in weeks), and randomized treatment-by-time interaction. Patient will be included as a random effect. The analysis will be stratified by the randomization strata. An unstructured covariance matrix will be assumed; if convergence issues arise, the following covariance structures will be employed in order until convergence is reached: heterogeneous Toeplitz, heterogeneous Compound Symmetry, heterogeneous first-order, auto-regressive, Toeplitz, Compound Symmetry, and first-order, auto-regressive. The treatment effect will be the contrast between sparsentan and irbesartan least squares (LS) means at Week 36. The LS means, treatment effect estimate (difference in LS means), 95% CI, and two-sided p-value will be extracted from the model. Results will be back-transformed to present treatment effects on the ratio scale.

### **12.7.2. Analysis of Key Secondary Efficacy Endpoints**

#### **12.7.2.1. Rate of Change in eGFR Following the Acute Effect of Randomized Therapy**

The rate of change in eGFR over 52 and 104 weeks (ie, following the acute effect of randomized therapy; see Section 12.7.4) will each be analyzed via a mixed-model random coefficients analysis. Utilizing eGFR data from (i) Weeks 6 to 58 and (ii) Weeks 6 to 110, eGFR will be the dependent variable with random patient effects for intercepts and slopes. Fixed effects for randomized treatment, baseline eGFR, time (in weeks), and randomized treatment-by-time interaction will be included. The analysis will be stratified by the randomization strata. An unstructured covariance matrix will be assumed; if convergence issues arise, a first-order, auto-regressive structure will be used. The treatment effect will be the contrast between sparsentan and irbesartan marginal slope estimates. The associated slope estimates, difference in slopes, 95% CI, and two-sided p-value will be extracted from the model. Slope and the difference in slopes will be annualized for ease of presentation and interpretation.

### **12.7.2.2. Rate of Change in eGFR Following Initiation of Randomized Therapy**

The rate of change in eGFR 110 weeks (ie, following initiation of randomized therapy) will each be analyzed via a mixed-model random coefficients analysis. Utilizing eGFR data from Day 1 to Week 110, eGFR will be the dependent variable with random patient effects for intercepts and slopes. Fixed effects for randomized treatment, baseline eGFR, time (in weeks), and randomized treatment-by-time interaction will be included. The analysis will be stratified by the randomization strata. An unstructured covariance matrix will be assumed; if convergence issues arise, a first-order, auto-regressive structure will be used. The treatment effect will be the contrast between sparsentan and irbesartan marginal slope estimates. The associated slope estimates, difference in slopes, 95% CI, and two-sided p-value will be extracted from the model. Slope and the difference in slopes will be annualized for ease of presentation and interpretation.

### **12.7.2.3. Type I Error Control for Efficacy Endpoints – Double-blind Period**

At the time of the primary analysis of change from baseline in UP/C, approximately 222 patients are projected to have eGFR data up to 58 weeks. If the analysis of UP/C at Week 36 yields a two-sided p-value <0.05, analysis of the key secondary endpoints will proceed.

[figure not shown]
For non-US countries, at the time of primary analysis of proteinuria, the key secondary endpoint of rate of eGFR rate of change over 6 to 58 weeks will be formally assessed at the 1% two-sided alpha level. Type I error control for the additional key secondary endpoints at confirmatory analysis will be governed at this time by a gate-keeper on the 6- to 58-week eGFR rate of change at the 1% level. The subsequent key secondary (confirmatory) endpoint analyses of eGFR rate of change over 6 to 110 weeks and eGFR rate of change over 110 weeks following initiation of randomized therapy will be tested sequentially and be assessed at the 4% two-sided alpha level if the 6- to 58-week eGFR rate of change analysis fails to achieve  $p < 0.01$ ; otherwise, subsequent key secondary (confirmatory) endpoint analyses will be assessed at the 5% two-sided alpha level.

For the US, at the time of primary analysis of proteinuria, the endpoint of rate of change over 58 weeks will not be formally tested. The key secondary (confirmatory) endpoint analyses of eGFR rate of change over 110 weeks following initiation of randomized therapy and eGFR rate of change over 6 to 110 weeks will be tested sequentially and assessed at the 5% two-sided alpha level.

The 2 confirmatory endpoints are intended to support regulatory submissions in the US (rate of change in eGFR over 110 weeks following initiation of randomized therapy) and non-US countries (6- to 110- week eGFR rate of change); hence, no further multiplicity adjustment is necessary. The Type I error control framework for the primary proteinuria and key secondary endpoints for US and non-US countries are displayed in [Figure 5](#). At the time of the final analysis, if all the key secondary endpoints achieve statistical significance, the other secondary endpoints will be statistically tested at the available alpha. For all other supportive efficacy endpoints, nominal p-values will be presented without Type I error control.

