##### **6.1.1.2. Key Secondary Efficacy Endpoints**

The secondary efficacy endpoints (see [Section 12.7.2](#)) are as follows:

- The rate of change in eGFR over a 52-week (approximately 1 year) period following the initial acute effect of randomized therapy (the initial acute effect of randomized therapy is defined as the first 6 weeks of randomized treatment with study medication; thus, the analysis is from 6 weeks post-randomization to 58 weeks post-randomization; eGFR chronic slope at 1 year).
- The rate of change in eGFR over a 104-week (approximately 2 years) period following the initial acute effect of randomized therapy (the initial acute effect of randomized therapy is defined as the first 6 weeks of randomized treatment with study medication; thus, the analysis is from 6 weeks post-randomization to 110 weeks post-randomization; eGFR chronic slope at 2 years).
- The rate of change in eGFR over a 110-week (approximately 2 years) period following the initiation of randomized therapy (thus, the analysis is from Day 1 to 110 weeks post-randomization; eGFR total slope at 2 years).

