Study visits will be conducted at 2, 4, 6, and 12 weeks after randomization and at approximately 12-week intervals thereafter. Following the 110-week blinded treatment period, treatment with study medication will be discontinued for 4 weeks. At this time, the Investigator should resume standard-of-care treatment, including RAAS inhibitor treatment. Where possible, the same treatment regimen the patient was on at study entry (ie, the same ACEI and/or ARB at the same dose[s]) should be used unless, in the Investigator's opinion, an alternative treatment approach is warranted. The Investigator may make additional adjustments in anti-hypertensive medications if considered necessary to adequately control blood pressure. Patients will return to the site for the Week 114 visit after study medication has been discontinued (see [Table 1](#) and [Section 15.1](#)).

[figure not shown]
Patients who complete the double-blind period may be eligible to enroll in the open-label extension period.

Sparsentan or irbesartan concentrations (and possibly metabolites) in plasma will be evaluated. At specified visits, 1 trough sample will be obtained pre-dose in the clinic.

The primary analysis of proteinuria will be performed after the last patient randomized has undergone the Week 36 visit. Subsequently, all patients will continue to be followed on an intent-to-treat basis to Week 114 for the longer-term assessment of eGFR rate of change. Unless otherwise specified, endpoints will use the last pre-treatment value available prior to the first dose of study medication as baseline.

Flow chart and table depicting the double-blind period are provided in [Figure 1](#) and [Table 1](#).

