### 12.2. Sample Size Justification

The hypothesis to be tested relating to the change in proteinuria at Week 36 post-randomization is as follows:

$$H_0: \Delta = 0 \text{ versus } H_1: \Delta \neq 0$$

where  $\Delta$  is the true difference between sparsentan and irbesartan in the log change from baseline in proteinuria at Week 36. Based on data from the Leicester University Hospital Registry of IgA nephropathy patients (Leicester IgAN Patient Registry) in over 350 patients with IgAN (who were not treated with steroid therapy) provided by [name], together with proteinuria data published by Inker et al (Inker 2016), the standard deviation of the log change from baseline in proteinuria at Week 36 is estimated to be 0.92. A total of 280 randomized patients will, therefore, provide at least 90% power to test that the true relative treatment effect on proteinuria, sparsentan versus irbesartan, is at least 30%. Based on the data published in Inker, this degree of treatment effect is predicted to reflect a treatment effect on clinical outcomes (doubling of serum creatinine, ESRD, or death) with a hazard ratio of 0.36 and a 95% confidence interval (CI) of (0.22, 0.61). In addition, [name] patient registry database indicates that a 30% treatment effect on proteinuria at the patient level predicts a difference in the slope of eGFR decline that translates to an estimated difference in eGFR at 104 weeks (approximately 2 years) of 6.64 mL/min/1.73 m^2, with a 95% CI of (0.83, 12.44).

Approximately 380 patients will be required to detect an underlying treatment effect in the rate of change in eGFR over 110 weeks following the initiation of randomized therapy (eGFR total slope at 2 years) of 2.9 mL/min/1.73 m^2 per year with 90% power. In addition, approximately 380 patients provide 80% power to detect a smaller treatment effect on eGFR total slope at 2 years of 2.55 mL/min/1.73 m^2 per year. Consequently, approximately 380 patients provide more than 90% power to detect an underlying treatment effect in the rate of change in eGFR over 104 weeks following the initial acute effect of randomized therapy (eGFR chronic slope at 2 years) of 3.15 mL/min/1.73 m^2 per year. With this sample size, the observed annualized treatment difference to yield a p-value of <0.02 is 1.8 mL/min/1.73 m^2 per year. These sample size and power calculations follow the method described by Dupont (Dupont 1998), with

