one-sided  $\alpha = 0.02$  and residual error of 5.8 mL/min/1.73 m^2 estimated from a random coefficient analysis of the Leicester University Hospital Registry. The projected treatment effects on the rate of change in eGFR were based on a meta-analysis of clinical studies in IgAN using the methodology presented by Inker ([Inker 2019](#)).

To investigate the safety and efficacy of SGLT2 inhibitors in combination with sparsentan on proteinuria in patients with IgAN, as compared to sparsentan alone, approximately 30 patients in each of the two treatment groups (total 60 patients) will be enrolled in the Sub-study. The sample size of the Sub-study is determined empirically without formal statistical assumptions.

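### Does the non-US 1-year eGFR slope test need its own power statement, or to be dropped, because about 222 patients at a two-sided 1% level give limited power?

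*Protocol*

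**What the plan says.** Protocol 6.1.1.2 lists as its first key secondary endpoint "The rate of change in eGFR over a 52-week (approximately 1 year) period following the initial acute effect of randomized therapy", that is, Week 6 to Week 58. For non-US countries, Protocol 12.7.2.3 says the "eGFR rate of change over 6 to 58 weeks will be formally assessed at the 1% two-sided alpha level"; SAP 8.4.1 has the same test, and both place it alongside the Week 36 proteinuria analysis. At that point "approximately 222 patients are projected to have eGFR data up to 58 weeks". SAP 8.2 restricts the test to patients who completed Week 58, plus early terminators whose schedule would have reached it. After a failed test, the later non-US slope tests are "assessed at the 4% two-sided alpha level if the 6- to 58-week eGFR rate of change analysis fails to achieve" significance at 1%; after a successful one they use 5%. The US procedure does not formally test the 1-year slope.

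The synopsis, Protocol 12.2 and SAP 4.3.1 give slope power for 2 years only, with about 380 patients, one-sided alpha 0.02 and residual error 5.8:

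- total slope: 90% power at 2.9 per year and 80% at 2.55;
- chronic slope: "approximately 380 patients provide more than 90% power to detect an underlying treatment effect in the rate of change in eGFR over 104 weeks", for a difference of 3.15 per year;
- smallest significant observed difference: 1.8 per year.

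The residual error was "estimated from a random coefficient analysis of the Leicester University Hospital Registry". No slope SD is given, and no effect size, power or detectable difference is given for the 1-year test.

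**The concern.** A formally tested key secondary endpoint has fewer patients than the powered analyses, about half the follow-up and a stricter significance level, yet no power is stated for it. A slope is estimated much less precisely over one year than over two, so a reader may suspect that the test is likely to fail even if the drug works as the design assumes.

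Two things seem to be at stake. A non-significant early result might be taken as no effect on kidney function. A failure also costs the non-US 2-year tests 1% of alpha. If the test had little chance of success and a real cost, there would be a case for dropping it, as the US procedure does.

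**Working it through.** **Inputs.** From Protocol 12.2: residual SD 5.8, one-sided alpha 0.02, about 380 patients. From Protocol 12.7.2.3: two-sided 1%, 222 patients (111 per arm at 1:1). From Protocol Table 1: visits at Weeks 6, 12, 24, 36, 48 and 58. From Protocol 12.7.2.1: "eGFR will be the dependent variable with random patient effects for intercepts and slopes". Two assumptions are added: the 2-year chronic effect of 3.15 applies in year 1, and data are complete. Years are weeks/52.

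**Step 1: the stated 2-year figures.** The standard error implied by an effect and its power is effect/(z0.98 + z_power).

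- 2.9/(2.054 + 1.282) = 0.869
- 2.55/(2.054 + 0.842) = 0.881
- 1.8/2.054 = 0.876

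The three agree, so the 2-year power statement is internally consistent.

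**Step 2: the 1-year test under the planned model.** The sum of squares of the six visit times about their mean is 0.768 years², so residual error adds 5.8²/0.768 = 43.8 to the variance of each patient's slope. With slope SD τ:

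SE = √[(2/111)(τ² + 43.8)], critical difference = 2.576 × SE, power = Φ(3.15/SE − 2.576).

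| τ | SE | Critical difference | Power at 3.15 |
|---|---|---|---|
| 0 | 0.888 | 2.29 | 83% |
| 3 | 0.975 | 2.51 | 74% |
| 5 | 1.113 | 2.87 | 60% |
| 6 | 1.199 | 3.09 | 52% |
| 8.2 | 1.414 | 3.64 | 36% |
| 10 | 1.610 | 4.15 | 27% |

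Power passes 80% only for τ up to about 1.8, and 50% for τ up to about 6.3. With 222 patients it does not reach 90%.

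**Step 3: can the documents narrow this range?** Not reliably.

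- *Back-solving τ.* An SE of 0.876 with 190 per arm implies a per-patient slope SD of 0.876 × √(190/2) = 8.54. Removing the residual part over the 2-year visits leaves τ of about 8.2, hence 36%. This treats the sponsor's calculation as if it used the planned model, which the documents do not say.
- *One value per patient.* SE = 5.8 × √(2/n)/(SD of visit times). For Weeks 6–58 (SD 0.358, n = 111) this gives SE 2.18 and power 13%. Its support is that, with the Week 6–110 visits (SD 0.676, n = 190), it returns 2.94, 2.55 and 1.81, close to the stated figures. But 2.9 and 2.55 are stated for the total slope from Day 1. With the Day 1–110 visits (SD 0.748), SE = 0.796 and the formula gives 2.65, 2.30 and 1.63. The match therefore needs a different window from the one stated, and one value per patient is not the planned analysis.
- *Sample size only.* Scaling the SE from 380 to 222 patients, with no allowance for shorter follow-up, gives 0.869 to 0.881 × √(380/222) = 1.137 to 1.153, and power 58% to 56%.

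**Step 4: cost to the 2-year tests.** One-sided 0.02 is the two-sided 4% that applies if the 1-year test fails. At SE 0.876:

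- two-sided 5%: critical difference 1.960 × 0.876 = 1.72; power at 3.15 is 95%;
- two-sided 4%: critical difference 2.054 × 0.876 = 1.80; power at 3.15 is 94%.

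The stated 2-year power is therefore already the power after a failed 1-year test.

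**The case for a change.** The strongest case for a change is that the shortfall against 90% does not hinge on the missing slope SD. Even if all patients declined at the same rate within an arm, power would be 83%, and a model with random slopes presupposes that they do not. The endpoint is listed first among the key secondaries, it is the only eGFR result formally tested at that time for non-US countries, and a power statement with a line on interpretation would be cheap.

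The arithmetic stands, and so does the observation that the documents are silent. Three parts do not stand.

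- That the test fails more often than not at 3.15 is true only for a slope SD above about 6.3, and no document supplies that SD.
- The 90% yardstick is brought in from outside: the plan claims no power for this test. The shortfall is also tied to 222, which the protocol calls approximate and projected. At slope SD 0, 280 patients would give 92% and 380 would give 98%. Protocol 6.2.1 times the proteinuria analysis after the last randomized patient's Week 36 visit, so the number could be higher.
- A failed test is unlikely to be reported as proof of no effect. Protocol 12.7.2.1 and SAP 8.6.1 already require the slope difference with its 95% CI, and formal 2-year tests follow whatever the 1-year result.

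**Conclusion.** The concern describes an omission correctly but does not justify a change. If 3.15 per year holds in year 1, residual error is 5.8, and 222 patients have complete data at six visits, power is at most 83%: 60% at slope SD 5, 36% at 8.2 and 27% at 10. Missing data would generally lower these values, and more patients would raise them.

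No printed figure is wrong. The power claims are confined to the 2-year slopes, agree with one another, and already use the level that applies after a failed 1-year test. A power sentence for the 1-year test would inform readers but would alter no analysis, decision rule or enrolment target. Dropping the formal test would recover about 1 percentage point of 2-year power at 3.15 (94% to 95%) and give up an early claim with a chance of success of 27% to 83% over slope SDs from 10 to 0. Either choice is defensible, and a non-US regulatory reason for keeping the test may exist outside these documents. The testing rule can stay as written.

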**Figure 5. Type I Error Control for the Primary and Key Secondary Efficacy Endpoints**

Abbreviations: eGFR = estimated glomerular filtration rate; US = United States

### 12.7.3. Primary and Sensitivity Analyses to Address Missing Data in the Primary and Key Secondary Efficacy Endpoints

For the primary analysis of the primary endpoint and key secondary endpoints of eGFR change from baseline and slope, missing data will be imputed using the multiple imputation procedure (Ouyang 2017; Rubin 1987). The SAP will provide full detail of the methodologies that will be used to execute primary and sensitivity analyses to assess the influence of missing primary and/or key secondary endpoint data. Briefly, these methodologies will include multiple imputation under an assumption of missing not at random and tipping-point analyses to explore how extreme the difference between randomized treatments would have to be among patients with missing data to overwhelm the treatment effect obtained in the primary and key secondary endpoint analyses described above. In these analyses, the multiple imputation approach will be expanded to allow for varying impact of missing data by incorporating a shift parameter in the imputation model. The range of values for the shift parameter will explore the varying missing data assumptions, including the scenario where the imputation model is completely based on the control group (ie, control-based imputation).

